9.1 Extent of Exposure

Exposure to IMP for randomized safety sample in open-label stabilization phase and double-blinded randomized withdrawal phase will be summarized in percentage of subjects' exposure and average daily dose for each week by treatment group in randomized phase. Exposure to IMP for open-label safety sample during open-label stabilization phase will be also provided in percentage of subjects' exposure and average daily dose by week.

9.2 Adverse Events

All adverse events (AEs) are coded by system organ class and Medical Dictionary for Regulatory Activities (MedDRA) preferred term (Version 23.0 or later). A treatment-emergent AE (TEAE) is defined as an AE which starts after start of trial medication (Aripiprazole IM depot/Oral tablets), or an AE continues from baseline of the specific phase and becomes serious, trial drug-related or results in death, discontinuation, interruption or reduction of study medication during this phase. The incidences of the following treatment-emergent adverse events (TEAEs) will be summarized by treatment group for the safety samples:

- TEAEs by severity
- Potentially drug related TEAEs
- TEAEs with an outcome of death
- Serious TEAEs
- Discontinuations due to TEAEs
- Death
- Non- Serious TEAEs

Deaths, SAEs, and AEs leading to discontinuation from the trial will be listed for the safety samples.

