1.2.2 Trial 31-12-294

The primary purpose of this phase 3, multicenter, open-label trial was to evaluate the long-term safety and tolerability of aripiprazole once-daily treatment with oral tablets in children and adolescents (7 - 17 years of age) with a diagnosis of TD. The secondary purpose was to evaluate the efficacy of once-daily aripiprazole in the suppression of tics in children and adolescents with a diagnosis of TD, as measured by change from baseline to Week 52 on the TTS of the YGTSS.

Subjects who successfully completed Trial 31-12-293 were eligible to enter this extension trial, provided that continuation of treatment was clinically warranted, as judged by the investigator, and there had been no significant protocol violations or clinically relevant AEs that would preclude their inclusion in the trial.

Aripiprazole was generally well tolerated in this trial. The safety and tolerability of aripiprazole, as demonstrated in this trial, was reflected in no subjects experiencing a fatal serious adverse event (SAE), 4 subjects experiencing nonfatal SAEs (none deemed related to investigational medicinal product [IMP]), and 10 subjects experiencing treatment-emergent adverse events (TEAEs) leading to IMP discontinuation (5 subjects

Protocol 31-14-204

for the event of weight increased). In addition, 40.0% and 31.8% of subjects overall experienced mild and moderate TEAEs, respectively, with 4.5% of subjects experiencing severe TEAEs. Fifty-six subjects (50.9%) had TEAEs that the investigator considered potentially related to IMP, with the events of weight increased, somnolence, and fatigue accounting for 45 of these subjects.

The efficacy analyses demonstrated that once-daily aripiprazole, as shown in the parent Trial 31-12-293, is effective in the treatment of tics associated with TD in children and adolescents (aged 7 - 18 years). In addition, these analyses demonstrated that subjects not currently taking aripiprazole, versus subjects with prior exposure (ie, subjects who received aripiprazole in Trial 31-12-293), yielded greater improvement in TD symptoms as measured by YGTSS TTS, CGI-TS change and severity scores, and total YGTSS score.

In summary, the data from this 52-week extension trial of subjects who participated in the parent Trial 31-12-293 demonstrated a favorable safety and tolerability profile of aripiprazole once-daily treatment in children and adolescents and its efficacy in the suppression of tics in this population.

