- Pregnancies are also defined as IREs. Although normal pregnancy is not an AE, it will mandate IMP discontinuation and must be reported on an IRE form to the sponsor. Pregnancy will only be documented on the AE eSource page if there is an abnormality or complication.

Clinical Laboratory Test Value Changes: It is the investigator's responsibility to review the results of all laboratory tests as they become available. This review will be documented by the investigator's dated signature on the laboratory report. For each abnormal laboratory test result, the investigator needs to ascertain if this is an abnormal (ie, clinically significant) change from baseline for that individual subject. This determination, however, does not necessarily need to be made the first time an abnormal value is observed. The investigator may repeat the laboratory test or request additional tests to verify the results of the original laboratory tests. If this laboratory value is considered medically relevant by the investigator (subject is symptomatic, requiring corrective treatment or further evaluation), or if the laboratory value leads to discontinuation, and/or fulfills a seriousness criterion, this is considered an AE.

Severity: Adverse events will be graded on a 3-point scale and reported as indicated on the eSource. The intensity of an adverse experience is defined as follows:

- 1 = Mild:** Discomfort noticed, but no disruption to daily activity.
- 2 = Moderate:** Discomfort sufficient to reduce or affect normal daily activity.
- 3 = Severe:** Inability to work or perform normal daily activity.

IMP Causality: Assessment of causal relationship of an AE to the use of the IMP is defined as follows:

- Related:** There is a reasonable possibility of a temporal and causal relationship between the IMP and the AE.
- Not Related:** There is no temporal or causal relationship between the IMP and the AE.

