- CT-5.5.2 Clinical Global Impressions Scale for Tourette's Syndrome (CGI-TS) Improvement Score - Mean by Week - OC (ITT Sample)
- CT-6.1.1 Simpson-Angus Scale Total Score - Mean Change from Baseline by Week - OC (Randomized Safety Sample)
- CT-6.1.2 Barnes Akathisia Rating Scale Global Score - Mean Change from Baseline by Week - OC (Randomized Safety Sample)
- CT-6.1.3 AIMS Movement Rating Score - Mean Change from Baseline by Week - OC (Randomized Safety Sample)
- CT-6.2.1 Columbia-Suicide Severity Rating Scale (C-SSRS) (children's version) - Suicidality (Randomized Safety Sample)
- CT-6.2.2 Columbia-Suicide Severity Rating Scale (C-SSRS) (children's version) by Type (Randomized Safety Sample)
- CT-7 Extent of Exposure to Investigational Medicinal Products Double-Blind Randomized Withdrawal Phase (Randomized Safety Sample)
- CT-8.1 Adverse Events (All Causalities) (Randomized Safety Sample)

- CT-8.2.1 Incidence of Treatment-Emergent Adverse Events by System Organ Class and MedDRA Preferred Term (Randomized Safety Sample)
- CT-8.2.2 Incidence of Treatment-Emergent Adverse Events by System Organ Class, MedDRA Preferred Term and Severity (Randomized Safety Sample)
- CT-8.2.3 Incidence and Occurrence (Number of Events) of non-Serious Treatment-emergent Adverse by System Organ Class and MedDRA Preferred Term (Randomized Safety Sample)
- CT-8.3.1 Incidence and Occurrence (Number of Events) of Potentially Drug-Related Treatment-Emergent Adverse Events by System Organ Class and MedDRA Preferred (Randomized Safety Sample)
- CT-8.3.2 Incidence of Potentially Drug-related Treatment-emergent Adverse Events by System Organ Class and MedDRA Preferred Term and Severity (Randomized Safety Sample)
- CT-8.4 Incidence of Deaths Due to Treatment-Emergent Adverse Events by System Organ Class and MedDRA Preferred Term (Randomized Safety Sample)
- CT-8.5.1 Incidence and Occurrence (Number of Events) of Serious Treatment-Emergent Adverse Events by System Organ Class and MedDRA Preferred Term (Randomized Safety Sample)
- CT-8.5.2 Incidence of Serious Treatment-emergent Adverse Events by System Organ Class and MedDRA Preferred Term and Severity (Randomized Safety Sample)
- CT-8.6.1 Incidence of Treatment-Emergent Adverse Events Resulting in Discontinuation from Trial by System Organ Class and MedDRA Preferred Term (Randomized Safety Sample)

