- CT-13.2.1 Columbia-Suicide Severity Rating Scale (C-SSRS) (children's version) - Suicidality (Open-Label Safety Sample)

- CT-13.2.2 Columbia-Suicide Severity Rating Scale (C-SSRS) (children's version) by Type (Open-Label Safety Sample)
- CT-14 Extent of Exposure to Investigational Medicinal Products in Open-Label Stabilization Phase (Open-Label Safety Sample)
- CT-15.1 Adverse Events (All Causalities) (Open-Label Safety Sample)
- CT-15.2.1 Incidence and Occurrence of Treatment-Emergent Adverse Events by System Organ Class and MedDRA Preferred Term (Open-Label Safety Sample)
- CT-15.2.2 Incidence of Treatment-Emergent Adverse Events by System Organ Class, MedDRA Preferred Term and Severity (Open-Label Safety Sample)
- CT-15.3.1 Incidence and Occurrence (Number of Events) of Potentially Drug-Related Treatment-Emergent Adverse Events by System Organ Class and MedDRA Preferred (Open-Label Safety Sample)
- CT-15.3.2 Incidence of Potentially Drug-Related Treatment-Emergent Adverse Events by System Organ Class, MedDRA Preferred Term and Severity (Open-Label Safety Sample)
- CT-15.4 Incidence of Deaths Due to Treatment-Emergent Adverse Events by System Organ Class and MedDRA Preferred Term (Open-Label Safety Sample)
- CT-15.5.1 Incidence and Occurrence (Number of Events) of Serious Treatment-Emergent Adverse Events by System Organ Class and MedDRA Preferred Term (Open-Label Safety Sample)
- CT-15.5.2 Incidence of Serious Treatment-Emergent Adverse Events by System Organ Class, MedDRA Preferred Term and Severity (Open-Label Safety Sample)
- CT-15.6.1 Incidence of Treatment-Emergent Adverse Events Resulting in Discontinuation from Trial by System Organ Class and MedDRA Preferred Term (Open-Label Safety Sample)
- CT-15.6.2 Incidence of Treatment-Emergent Adverse Events Resulting in Discontinuation from Trial by System Organ Class, MedDRA Preferred Term and Severity (Open-Label Safety Sample)
- CT-15.7 Incidence and Occurrence (Number of Events) of Non-Serious Treatment-Emergent Adverse Events by System Organ Class and MedDRA Preferred Term (Open-Label Safety Sample)
- CT-16.1.1 Laboratory Test Results for Serum Chemistry - Mean Change from Baseline (Open-Label Safety Sample)
- CT-16.1.2 Laboratory Test Results for Hematology - Mean Change from Baseline (Open-Label Safety Sample)
- CT-16.1.3 Laboratory Test Results for Urinalysis - Mean Change from Baseline (Open-Label Safety Sample)

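### The TEAE definition in SAP 9.2 omits worsening in severity and is not tied to the phase's first dose, so the double-blind TEAE tables do not isolate what emerged or worsened after randomization

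*SAP*

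**What the plan says.** SAP 9.2 is the only place in the two documents that defines a TEAE. Protocol 7.6.1.1 and 7.6.1.2 list TEAE summaries for each phase but use the term without defining it.

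The SAP definition has two routes.

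- **Onset:** an event "which starts after start of trial medication (Aripiprazole IM depot/Oral tablets"). The anchor is trial medication as a whole, not the first dose of a phase.
- **Carry-over:** "an AE continues from baseline of the specific phase and becomes serious, trial drug-related or results in death, discontinuation, interruption or reduction" (the last three concern the IMP, and the change must fall within that phase). The list is closed, and an increase in severity is not on it.

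Severity is collected and reported. Protocol 5.1 says "Adverse events will be graded on a 3-point scale and reported as indicated on the eSource", with grades of mild, moderate and severe. SAP 9.2 plans "TEAEs by severity", and Appendix 4 carries this through for both phases: "CT-8.2.2 Incidence of Treatment-Emergent Adverse Events by System Organ Class, MedDRA Preferred Term and Severity (Randomized Safety Sample") and "CT-15.2.2 Incidence of Treatment-Emergent Adverse Events by System Organ Class, MedDRA Preferred Term and Severity (Open-Label Safety Sample").

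On recording, Protocol 5.7.1 asks for the current status of a nonserious event, ongoing or resolved. Neither document says whether a change of grade opens a new record.

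**The concern.** This is a randomized withdrawal design. The earliest randomization is at open-label Week 14 and the latest at Week 20, so every child reaches randomization after weeks of known aripiprazole. Some events will be ongoing at that point. The randomized safety comparison should show what happens next on full dose, half dose or placebo: which events are new, and which carried-over events get worse.

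A TEAE rule serves that purpose only if it is anchored to the phase and responds to worsening. This one does neither clearly. Safety and tolerability is the secondary objective. Because the trial ended early and SAP 8.1.1 and 14 reduce efficacy to descriptive summaries, the AE tables are a substantial part of what the randomized phase will report. Two programmers working from SAP 9.2 could also produce different versions of CT-8.2.1.

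**Working it through.** No sample size, power or alpha figure is involved, so the check is one of logic.

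**Step 1. Can another carry-over trigger stand in for worsening?** Take a nonserious event that began open-label and goes from mild to moderate after randomization.

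- Serious, death: not met, by construction.
- Drug-related: the event has to become related. One already judged related in the open-label phase cannot do so again.
- Reduction: SAP 3.2.2 allows no dose adjustment in the double-blind phase. This is harmless in itself, because the same definition also serves the open-label phase, where down-titration exists.
- Discontinuation or interruption: met only if the worsening leads to it.

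So a plain mild-to-moderate worsening meets none of them.

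**Step 2. How is each kind of event classified in the double-blind phase?**

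| Event | Onset route applied by phase | Onset route read literally |
|---|---|---|
| A. Began open-label, ongoing at randomization, unchanged | Not a double-blind TEAE | Already a TEAE; can be counted under the randomized arm |
| B. As A, but mild to moderate after randomization, same record, no other trigger | Not a double-blind TEAE: the worsening is left out | Already a TEAE because of its open-label onset, exactly as A |
| C. As B, but worsening entered as a new record | TEAE | TEAE |
| D. As B, but becomes serious or newly related, or leads to discontinuation or interruption | TEAE by carry-over | TEAE |
| E. Onset after the first double-blind dose | TEAE | TEAE |

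Applied by phase, the rule misses B. Read literally, it admits A together with B, so incidence does not separate unchanged open-label events from worsened ones, and the placebo arm can carry events that began on aripiprazole. The SAP does not say which reading governs. It also does not say to which phase an open-label-onset event continuing past randomization belongs.

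**Step 3. Is a phase anchor available?** Yes. SAP 3.4 already computes Trial Day from the IMP dosing date in the corresponding phase.

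**Step 4. Scale.** The planned arm size is 38 (SAP 4). One subject counted or not counted moves an arm's incidence by 1/38 = 0.026, or 2.6 percentage points. Actual arm sizes after early termination are not in the documents; with smaller arms the shift per subject would be larger. The number of subjects in rows A and B cannot be derived.

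**The case against.** The strongest reply is that the by-phase reading is the natural one. The carry-over route speaks of the specific phase, SAP 9 pairs each safety sample with its own phase, and Protocol 7.6.1.2 summarizes events during the withdrawal phase. This stands as a reason to doubt that open-label events would be counted under placebo. But it is the reading under which row B drops out, so it exchanges one fault for the other.

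Second, the omission is conditional. It needs the by-phase reading, a single continuing record, and no other trigger. This stands in full. A reader might infer that such an event is missing from the main AE tables altogether, and the documents do not support that. An event with onset after the first open-label dose is still counted in the open-label tables (CT-15.x). Table CT-8.1 and listing AE-1.2 are not limited to TEAEs by their titles. What is exposed is the double-blind TEAE tables from CT-8.2.x on.

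Third, a jump from mild to severe may already be caught. The severe grade in Protocol 5.1 overlaps the seriousness criterion about disruption of normal life functions, and seriousness is a trigger. This stands, and is why the example here is mild to moderate.

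Fourth, several domains are followed by change from baseline whatever the TEAE rule: extrapyramidal scales, weight and waist, laboratory values and ECG. Worsening suicidal ideation has its own definition in SAP 9.6.2. This narrows the gap, but symptoms such as somnolence and fatigue are followed only as AEs.

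Fifth, all safety output is descriptive, and no test or decision rule depends on TEAE counts. This limits the consequence but does not make the definition correct.

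**Conclusion.** The definition is deficient and should be corrected. It omits worsening in severity from the carry-over triggers and does not tie onset to the phase, and no other text in either document fills the gap. Depending on the reading, the double-blind TEAE tables either leave out carried-over events that only worsen in grade or can include events that began before randomization.

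The size is unknown. A reader might try to take it from the earlier 52-week extension, where Protocol 1.2.2 reports that "40.0% and 31.8% of subjects overall experienced mild and moderate TEAEs, respectively, with 4.5% of subjects experiencing severe TEAEs". Adding these gives 40.0 + 31.8 + 4.5 = 76.3% with any TEAE, and (40.0 + 31.8)/76.3 = 94% of those below severe. That does not measure the problem. The sum assumes exclusive worst-grade categories, which the protocol does not state, and it says nothing about events ongoing at randomization or worsening afterwards. Nor do the documents show that ongoing events are common at randomization: SAP 3.2.1 discontinues children who need down-titration after Week 8, which selects for tolerability.

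A reader might also link the IM depot wording to the omission. The product in this trial is oral tablets with matching placebo, so the phrase is an apparent carry-over that changes no classification.

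The conclusion about omission rests on one assumption the documents leave open, that a change of grade stays on the existing record.

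**What to change.** Rewrite the definition in SAP 9.2 by phase. Suggested content: for each phase, a TEAE is an AE with onset on or after the first dose of that phase's IMP, or an AE ongoing at that phase's baseline that, during the phase, increases in severity or meets one of the triggers already listed. Add that a severity increase is assigned to the phase in which it occurs, whether it is entered as a new record or as a change to an existing one.

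As a separate clean-up, delete the reference to an IM depot product.

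The cost is a couple of sentences and one derivation, with the TEAE tables in the CT-8 and CT-15 series rerun if they already exist. The downside is slightly more TEAEs reported. Data collection cannot be changed after the fact. If the AE records hold only one undated grade per event, the date of worsening cannot be recovered, and the report should say so and state which rule was applied.

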Subjects entering the double-blind randomized withdrawal phase will be randomized 1:1:1 to the half-dose arm, full-dose arm, or placebo arm. Doses in the aripiprazole arms will be based on the subject's stabilized dose during the single-blind stabilization phase. Subjects will be monitored for relapse during the double-blind randomized withdrawal phase. Relapse is defined as a loss of $\geq 50\%$ of the improvement experienced during the open-label stabilization phase (ie, improvement at the last assessment of YGTSS before randomization) on the YGTSS TTS. If a subject meets relapse criteria, they should be discontinued and treated according to the schedule of assessments.

There will also be a safety follow-up period (30 + 3 days) after the last dose of IMP or after the clinical site is notified that the subject prematurely discontinued their IMP.

During the pretreatment phase, modifications to a subject's pre-existing treatment are not to be made for the explicit purpose of entering this trial, but should be done only where deemed clinically appropriate by the investigator. Tapering rates for washout of medications are at the discretion of the investigator and are to be determined on an

Protocol 31-14-204

individual basis, with consideration to the subject's clinical condition, dose, and known pharmacokinetics (PK) of the medication being tapered, as long as the protocol-mandated discontinuation timeframe is met. The exception is a long-acting depot medication, which cannot be tapered and would be discontinued after the informed consent/assent is obtained.

[figure not shown]

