5.7 Follow-up of Adverse Events

For this trial, information on all AEs will be followed for up to 30 (+ 3) days after the last dose of IMP has been administered.

Protocol 31-14-204

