7.1 Sample Size

The planned sample size for the double-blind randomized withdrawal phase is 114 subjects (ie, 38 subjects per treatment group). Assuming the proportion of randomized subjects experiencing relapse during the double-blind randomized withdrawal phase will be 65% in the placebo group and 34% in each of the 2 aripiprazole dose groups, 114 subjects will provide approximately 80% power to detect a hazard ratio of 0.4 for relapse (either aripiprazole dose group versus placebo) at the alpha level of 0.05 (2-sided). Under the above assumptions, a total of 51 relapse events are expected to be observed during the randomization phase. However, subject enrollment will stop when 51 relapse events have accrued or 114 subjects have been randomized, whichever occurs earlier.

The sample size will allow one IA at approximately 70% of events accrual time point. The O'Brien-Fleming boundaries were used for sample size calculation of the interim analysis so that the interim analysis will be conducted when 36 relapse events occur.¹⁹ The 2-sided alpha levels for the IA is 0.016, and the alpha left for the final analysis will be 0.045.

In order to randomize 114 subjects, approximately 228 subjects will need to enter the open-label stabilization phase of the trial, assuming that the stabilization rate is 50%.

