9.5 Electrocardiogram Data

All ECG analyses are made using observed data. Baseline is defined as average of ECG measurements at baseline visit as specified in [Section 5.2](#). Last visit for each phase is defined as average of ECG measurements at last visit as specified in [Section 5.2](#). Missing ECG data will not be imputed. For the calculation of QT correction by heart rate, QTc is missing only if all three consecutive beats are unreadable. If there is at least 1 beat available in the lead, the data are included in the analysis. For each ECG, QT and RR

intervals from three consecutive complexes (representing three consecutive heart beats) are measured manually. The QT correction is performed on beat-to-beat basis. The mean of ratios (beat-to-beat) is calculated by $(QT_{c1} + QT_{c2} + QT_{c3})/3$ using each QT-RR pair: (QT1, RR1), (QT2, RR2) and (QT3, RR3). The corrected QT intervals for QT_{cB}, QT_{cF}, and QT_{cN} are defined as follows:

- QT_{cB} is the length of the QT interval corrected for heart rate by Bazett's formula: $QT_{cB} = QT / (RR)^{1/2}$.
- QT_{cF} is the length of the QT interval corrected for heart rate by Fredericia's formula: $QT_{cF} = QT / (RR)^{1/3}$.
- QT_{cN} is the length of the QT interval corrected for heart rate by the FDA Neuropharm Division formula: $QT_{cN} = QT/(RR)^{0.37}$.

Potentially clinically relevant ECG abnormalities will be listed by subject. Criteria for identifying ECG measurements of the potentially clinically relevance are provided in [Appendix 3](#). The incidences of abnormal ECGs of potential clinical relevance based on the observation at the scheduled and the unscheduled post-baseline visits will be tabulated the safety samples. Descriptive statistics of change from baseline in ECG intervals of PR, QRS, RR, QT, QT_{cB}, QT_{cF}, and QT_{cN} will be presented at each scheduled trial week and last visit for the safety samples.

In summarizing the incidence of abnormalities, a patient must have had an evaluation that meets abnormality criteria by the end of trial phase. Incidence rate is calculated as the number of patients having at least 1 abnormality within the corresponding study phase divided by the number of patients who are both exposed to study medication and have an on-treatment evaluation within the same study phase.

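### Double-blind adverse events are tabulated only as crude incidence by arm, although placebo subjects are expected to be observed for less time; an exposure-aware summary should be added

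*SAP*

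**What the plan says.** - **Relapse stops participation.** Protocol 3.1: "If a subject meets relapse criteria, they should be discontinued and treated according to the schedule of assessments". SAP 3.1.3 repeats this, and Protocol 3.8.3.3 lists relapse among the reasons for discontinuing IMP.
- **Relapse is expected to differ by arm.** Protocol 7.1 plans "114 subjects (ie, 38 subjects per treatment group") and assumes relapse in "65% in the placebo group and 34% in each of the 2 aripiprazole dose groups" over the 12-week double-blind phase.
- **Adverse events are reported as incidence.** SAP 9.2: "The incidences of the following treatment-emergent adverse events (TEAEs) will be summarized by treatment group for the safety samples". Protocol 7.6.1.2 does the same for the withdrawal phase. Tables CT-8.1 to CT-8.6.2 follow this, some adding the number of events. The only explicit definition of an incidence rate, for ECGs in SAP 9.5, is a count of patients "divided by the number of patients who are both exposed to study medication and have an on-treatment evaluation within the same study phase"; it has no time component.
- **Time on treatment is tabulated separately.** SAP 7.1 summarises duration in each phase by arm. SAP 9.1 gives percentage exposed and average daily dose by week and arm.
- **Not planned in either document:** a person-time rate, a time-to-first-event analysis of adverse events, or a between-arm safety test.

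**The concern.** A crude percentage answers how many subjects had an event while they were being watched. If one arm is watched for less time by design, its percentage is lower even when the underlying risk is the same. Here the arm expected to leave sooner is placebo, so the planned tables would tilt against both aripiprazole arms without any drug effect.

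Safety and tolerability are the trial's secondary objective, and the double-blind phase is the only placebo-controlled source of safety data. The side-by-side percentages are what readers will compare.

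**Working it through.** **Inputs.** 38 subjects per arm, 12-week relapse of 65% and 34%, hazard ratio 0.4 (Protocol 7.1); visits at Weeks 1, 2, 3, 4, 6, 8, 10 and 12 (SAP 3.1.3); adverse event follow-up of 30 days after the last dose (Protocol 5.7). The documents give no shape for the relapse hazard and no adverse event timing; both are assumptions, varied below.

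**1. The plan's own figures reproduce.** Protocol 7.1 says "114 subjects will provide approximately 80% power to detect a hazard ratio of 0.4 for relapse".
- Events: 38 × 0.65 + 2 × 38 × 0.34 = 50.54, i.e. the stated 51.
- Implied hazard ratio: ln(0.66)/ln(0.35) = 0.396, i.e. 0.4.
- Events in one pairwise comparison: 38 × (0.65 + 0.34) = 37.62. Schoenfeld power: Φ(√(37.62/4) × |ln 0.4| − 1.96) = 80.2%.

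**2. Observation time, constant relapse hazard.** λ = −ln(1 − p)/12; mean time = p/λ.
- Placebo: λ = 0.0875 per week, mean 7.43 weeks (about 282 subject-weeks for 38 subjects).
- Aripiprazole: λ = 0.0346 per week, mean 9.82 weeks (about 373 subject-weeks).
- Ratio 7.43/9.82 = 0.757, so 24.3% less time on placebo.

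**3. Other patterns.**

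| Assumption | Placebo (wk) | Aripiprazole (wk) | Less on placebo |
|---|---|---|---|
| Relapse recognised only at scheduled visits | 7.94 | 10.10 | 21.3% |
| Relapse times uniform: 12 × (1 − p/2) | 8.10 | 9.96 | 18.7% |
| Constant hazard, all subjects cut off uniformly over 0-12 weeks | 4.35 | 5.25 | 17.1% |
| Relapses average Week 2: 12(1 − p) + 2p | 5.50 | 8.60 | 36.0% |
| Relapses average Week 10: 12(1 − p) + 10p | 10.70 | 11.32 | 5.5% |

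Adding 10-30% non-relapse dropout, equal in all arms, to the constant-hazard case gives 23-24%.

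**4. Effect on crude incidence, same adverse event hazard in all arms.** For a 12-week risk q, g = −ln(1 − q)/12 and crude incidence = g/(g + λ) × [1 − exp(−12(g + λ))].

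| q | Placebo | Aripiprazole | Risk ratio |
|---|---|---|---|
| 10% | 6.2% | 8.2% | 1.31 |
| 20% | 12.6% | 16.5% | 1.31 |
| 40% | 25.9% | 33.3% | 1.29 |
| 60% | 40.1% | 50.6% | 1.26 |

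**5. Early events.** If adverse event risk is confined to the first w weeks, w replaces 12 in both formulas of step 4. With q = 20%: w = 2 gives 18.4% vs 19.3% (ratio 1.05); w = 4 gives 17.0% vs 18.7% (ratio 1.10).

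**6. If the follow-up month counts.** Adding 30/7 = 4.29 weeks to each arm gives 11.72 vs 14.10 weeks, 17% less on placebo (15% with visit-detected relapse), and a risk ratio of about 1.13-1.20.

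**7. Which adjusted measure.** Take step 5 and divide first events by the whole double-blind time at risk.
- w = 4: placebo 16.99% over 6.29 weeks = 2.70 per 100 subject-weeks; aripiprazole 18.72% over 8.22 weeks = 2.28; ratio 0.84.
- w = 2: placebo 18.41%/6.13 = 3.00; aripiprazole 19.35%/8.04 = 2.41; ratio 0.80.

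Both are further from 1 than the crude 1.10 and 1.05. A Kaplan-Meier estimate of first-event incidence recovers the same q in each arm whatever the timing, provided adverse event risk is independent of relapse.

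**The case against.** The strongest reply has four parts.

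- **Descriptive safety.** No arm is tested against another. True, but the percentages still stand side by side.
- **The imbalance is already shown.** SAP 7.1 and 9.1 give duration and weekly exposure by arm, and some CT-8 tables add event counts. This stands as mitigation: a careful reader can see the problem. It does not adjust the percentages.
- **The trial stopped early.** SAP 8.1.1 and 14 say so, and the randomised numbers and relapse rates are not in the documents. The 65% and 34% are planning values. Uniform truncation narrows the gap to 17% but does not remove it.
- **Size depends on timing.** This stands fully: for events soon after randomisation the distortion is small.

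A reader might go further and infer that placebo subjects' first 30 days are contaminated by open-label aripiprazole, so that the contrast could err in either direction. The documents do not support that. Protocol 5.7 says only that "information on all AEs will be followed for up to 30 (+ 3) days after the last dose of IMP has been administered". That is a safety follow-up period, not a stated carry-over window, and neither document gives data for a 30-day cut. The half-dose arm also steps down from its stabilised dose.

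Nor can the calculation be carried over to laboratory, vital sign and ECG abnormalities (SAP 9.3-9.5). Double-blind laboratory tests and ECGs are scheduled only at Week 4 and at Week 12 or early termination, and early leavers are asked to complete the end-of-treatment procedures. Detection there depends on the number of assessments rather than on person-time.

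**Conclusion.** The point holds for adverse events in the double-blind phase. Under the planning relapse rates placebo is observed for about 17-24% less time in the central scenarios. With no drug effect, aripiprazole looks worse on crude incidence in every scenario examined. A spurious risk ratio of about 1.3 requires roughly constant relapse and adverse event hazards and no follow-up events counted; it should not be read as a general inflation factor. These figures assume equal adverse event risk in all arms, independent of relapse, and the planning relapse rates rather than the observed ones.

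It would be too strong to call the planned tables uninterpretable, since the imbalance is visible elsewhere in the report. The gap is that nothing links exposure to the adverse event counts.

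A related ambiguity adds to it: the SAP 9.2 definition of a TEAE has no end date. The wording of Protocol 7.6.1.2 and the separate follow-up listing AE-1.3 suggest that follow-up events are excluded, but the SAP does not say so.

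**What to change.** In SAP 9.2 and Appendix 4:

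1. Keep the percentages. Add, by arm, the Kaplan-Meier cumulative incidence of first TEAE, overall and for the main categories, with time from first double-blind dose and censoring at end of double-blind treatment.
2. Show total subject-weeks per arm in CT-7, with events per 100 subject-weeks as a supplement only. A whole-phase rate can mislead when events cluster early (step 7 of the working).
3. State whether adverse events with onset in the 30-day follow-up count as double-blind TEAEs.

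No change to trial conduct or data collection is needed; the dates are already recorded. The cost is SAP wording and a few extra columns. The estimates will be imprecise because the trial stopped early, so they should sit beside the percentages rather than replace them. The Kaplan-Meier estimate still assumes that leaving at relapse is unrelated to adverse event risk, and a footnote should say so.
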